## Note to Applicants

Prior to completing your application form you should:

- Contact the eDRIS Team, who will assist you - [[contact]](mailto:[contact]) or by phone on [name]
- Read and understand the separate Guidance for Applicants

Your application should be typed, not handwritten. Your eDRIS application coordinator will inform you how to submit your application form and any supporting evidence. Before submitting your completed application, you should ensure that:

- All relevant sections of the application are complete
- Relevant supporting evidence is attached
- Individuals named on the form have read and approved its submission

Please note that submitted applications may be circulated to panel members, administrative colleagues, NHSScotland information governance and information security colleagues, Caldicott Guardians, the CHI Advisory Group and, where appropriate, non-NHS Scotland colleagues from a variety of participating partner bodies, in the course of processing. You must make your eDRIS application coordinator aware of any confidential or sensitive information contained in your application which you would consider inappropriate for circulation in such a manner. Your application could be subject to disclosure or partial disclosure under the Freedom of Information (Scotland) Act, and will be retained in line with NHSScotland information policy.

## Section 2 – Organisations & Bodies

2.1 Organisation or Body Leading Proposal Please read section 2.1 of the guidance		
2.1.01	Organisation or Body Name:  Dutch Adhesion Group  (Research workgroup linked to the Dutch college of gastro-intestinal surgeons and Dutch college of gynaecologists and obstetricians)	If the organisation here is an NHSScotland board, note this and go directly to question 2.1.4
2.1.02	Is this organisation or body a registered data controller? If 'Yes', provide Data Protection Registration Number:	No
2.1.03	Is this a commercial organisation or body?	No
2.1.03a	If 'Yes', please provide a full explanation of the organisation or body's activity and industry sector, including any previous experience of using NHSScotland data - append supporting documentation as appropriate	If applicable
2.1.04	Is this organisation or body wholly funding or paying for the costs of conducting the proposal?	Yes

2.2 Organisation or Body Funding Proposal Please read section 2.2 of the guidance		
Complete the following section if you answered 'No' to question 2.1.4		
2.2.01	Organisation or Body Name:	If the organisation here is an NHSScotland board note this and, go directly to section 2.3
2.2.02	Is this organisation or body a registered data controller? If 'Yes', provide Data Protection Registration Number:	No
2.2.03	Is this organisation or body a commercial organisation?	No
2.2.03a	If 'Yes', please provide a full explanation of the organisation or body's activity and industry sector, including any previous experience of using	

	NHSScotland data - append supporting documentation as appropriate	
--	---	--

**2.3 Other Relevant Organisations or Bodies** *Please read section 2.3 of the guidance**Complete this section if applicable*

Organisation Name	Nature of Business/Sector	Nature of interest in proposal
Radboud University Medical Center, Nijmegen, the Netherlands	University Medical Center	University supporting proposal and facilitating the applicant

### Section 3 – Overview

3.1	Proposal Essentials Please read section 3.1 of the guidance											
3.1.01	Proposal title/name:	Adhesion-related hospital readmissions after abdominal and pelvic surgery: An update of the SCAR studies										
3.1.02	Is this proposal an extension or renewal of an existing approval (for example to conduct a study over a wider geographic area or for a longer period of time)? Please provide details, include the reference number of the original approval, and summarise the changes requested	No										
3.1.03	Is this new proposal related to a previous application (approved or not)? Please give details, indicate if this is a resubmission, including the reference number of the original submission	No										
3.1.04	
What is(are) the substantive purpose(s) of the proposal? (tick all that apply)
 
 
  Patient Care	 Research	
 
  Audit	 Performance Monitoring/Management	
 
  Service Planning/Improvement	 Health/Social Care Administration	
 
  Systems Implementation/Testing	 Training/Education	
 
  Quality (Clinical, Educational, etc)		
 
 
If other clearly defined purpose, please give details:
		 Patient Care	 Research	 Audit	 Performance Monitoring/Management	 Service Planning/Improvement	 Health/Social Care Administration	 Systems Implementation/Testing	 Training/Education	 Quality (Clinical, Educational, etc)	
 Patient Care	 Research											
 Audit	 Performance Monitoring/Management											
 Service Planning/Improvement	 Health/Social Care Administration											
 Systems Implementation/Testing	 Training/Education											
 Quality (Clinical, Educational, etc)												
3.1.05	Does the proposal require the use of information which can identify or potentially identify individuals?	No										
3.1.06	Access is being requested to data from which sources? (tick as many as are relevant)											

- A single NHS Scotland Board (excluding NSS)
- NHS National Services Scotland
- More than one NHS Scotland Board
- A national NHS Scotland system/database
- More than one NHS Scotland system/database
- Community Health Index (CHI) database
- NHS Central Registry

If other, please give details:

**3.1.07** *Provide a full, clear concise outline of the proposal background – describe why it is needed, aims and objectives and envisaged benefits to the public and/or patients:*

Adhesion formation is the most common cause for long – term complications in abdominal surgery. Abdominal surgery is performed by a multitude of specialists, including general surgeons, gynaecologists, vascular surgeons and urologists. In Scotland, like many other developed countries, adhesion- related complications cause a huge burden of morbidity. Adhesion-related complications comprise various clinical entities such as small bowel obstruction, chronic pain and female infertility.

In 1999 [name] demonstrated in the SCAR studies, using data from the Scottish National Health Service record linkage database, that as many as 34.6% of patients undergoing abdominal surgery are readmitted for complications directly or possibly related to adhesion formation in 10 years after surgery.

Since this landmark study a number of strategies were introduced to reduce adhesion formation. First are the so-called 'anti-adhesion' barriers. Almost simultaneously there has been the rise of minimal invasive surgery. Minimal invasive surgery is associated with less extensive peritoneal injury and adhesion formation.

While minimal invasive surgery became adopted quickly, the use of anti-adhesion barriers remains marginal. Many surgeons therefore feel that with laparoscopy further adhesion prevention is not necessary, despite some evidence that incidence of adhesion- related complications is still considerable.

	
To evaluate the impact of laparoscopic surgery on adhesion- related formation, we are planning to perform an update of the SCAR studies to recent years in which a large number of laparoscopic surgeries have been performed. Comparison of readmissions for adhesion- related complications after open and laparoscopic surgery will be made. The study will provide an estimate of the current burden of adhesion-related morbidity in Scotland, which could also serve as a model for the current burden in other European countries. Further such estimate can be used to model the impact of further implementation of anti-adhesion barriers on adhesion-related morbidity and healthcare costs in both Scotland and abroad.

3.1.08	
Provide a full, clear and concise outline of the proposal design, listing: data sources; sample size ; inclusion/exclusion criteria (eg involvement in trial/survey; health event, etc); relevant date range; need for identifiable or potentially identifiable data; requirement for a matched control cohort etc.
 
We intend to use the Scottish National Health Service record linkage capabilities. Inclusion criteria are all patients undergoing initial abdominal or pelvic surgery between June 2009 and June 2011. Selection will be made by OPCS-4 codes related to the admission. A list of relevant codes can be found in the appendix. We choose for these years to allow inclusion of an incident population in a time that laparoscopic surgery had already been implemented and that allows for 4 to 5-years of follow-up.
 
We will exclude patient who had had abdominal or pelvic operation in the 5 years before 2009, as pre-existing adhesions from this prior surgery might influence results. There are no further exclusion criteria.
 
For analyses patients will be grossly divided in three groups of anatomical location of the surgery: hindgut, female reproductive tract, and foregut or other. Within each group subgroups of laparoscopic and open procedures will be made.
 
We expect approximately 70,000- 100,000 patients to have had abdominal or pelvic surgery in the period June 2009- June 2011. Approximately 25,000 are expected to have had prior abdominal surgery in the previous 5 years. Thus, we expect an incident population of 45,000 to 75,000 to be included in the study.

	
For the study we will analyse re-admission in the years following surgery that are directly related to adhesions, possibly related to adhesions, and readmission with surgery that might be complicated by adhesions. For this purpose we will need a patient identifier that allows to link readmissions to the initial surgery. The data can be anonymized so that the identifier represent just a random number. As baseline characteristics we will only require age and sex. No further potentially identifiable data such as birth date, postal code or NHS number is required.
 
From the initial admission with abdominal or pelvic surgery we need ICD- 10 codes and OPCS- 4 codes describing the type of surgery performed as well as information whether the operation was performed laparoscopic ally or open. This same set of information is needed for any readmission in follow-up. Further we need the time interval (in months) between the index operation and the readmission. Only readmissions coded by one or more relevant ICD-10 or OPCS-4 code need to be included.
 
For a readmission to be classified as directly related to adhesions, an explicit adhesion reference was required in the operative OPCS-4 or diagnostic ICD-10 coding. Adhesions might however not always be coded, especially not if readmission goes without surgery. For example, a conservative treated small bowel obstruction might only be coded as abdominal pain, nausea, and vomiting. Therefore we will define a broader set of operative codes and diagnostic codes that might indicate a possibly adhesion- related complication.
 
Data from follow-up is requested to the latest date from which a complete record can be extracted.

3.1.09	Does the proposal have implications for, or target, sensitive groups or vulnerable populations? Please give details
	No
3.1.10	Does the proposal seek to use information exclusively about deceased persons? Please give details
	No

3.1.11	Have any members of the public/lay representatives been involved in the proposal design? Please give details
	No
3.1.12	Has any peer review of the proposal been undertaken? Please give details (for example formal review by a peer organisation or funding body, informal internal review, review by a third party)
	Informal internal review has been performed within the Radboud University Medical Center, department of Surgery. The research proposal and internal funding for performing the study were approved.
3.1.13	Is there any commercial aspect or dimension to the proposal or its outcomes? Please give details
	No

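### The burden objective in 3.1.07 has no population limit, but the 3.1.08 cohort leaves out the 25–36% of surgical patients operated on within a five-year look-back

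*Combined protocol and SAP*

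**What the plan says.** Section 3.1.07 sets two aims. One is comparative: "Comparison of readmissions for adhesion- related complications after open and laparoscopic surgery will be made". The other is descriptive: "The study will provide an estimate of the current burden of adhesion-related morbidity in Scotland". The section adds that the estimate could stand as a model for other European countries, and that "such estimate can be used to model the impact of further implementation of anti-adhesion barriers on adhesion-related morbidity and healthcare costs". No population limit is attached to the descriptive aim.

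Section 3.1.08 defines one cohort for both aims, restricted to initial surgery: "We will exclude patient who had had abdominal or pelvic operation in the 5 years before 2009". The reason given is that adhesions left by the earlier operation could affect the findings; no direction or size is stated. Before this exclusion the plan counts on 70,000–100,000 operated patients in the two-year window. For those to be removed, the figure is: "Approximately 25,000 are expected to have had prior abdominal surgery in the previous 5 years". By the plan's subtraction, 45,000–75,000 remain as the study cohort.

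Section 4.3 describes the exclusion differently, counting the five years back from each patient's index operation.

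**The concern.** For the open versus laparoscopic comparison, removing recently operated patients is sensible, because it takes out a source of adhesions that the index approach did not cause. The burden aim inherits the same cohort, and there the restriction does something else. It removes a quarter to a third of the surgical population, and removes them because they may already carry the condition whose burden is being estimated.

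If the result is read as the national figure, it describes only patients with no recent earlier operation. A barrier or cost model that needs totals would start from an incomplete count. One that needs a per-patient risk would start from a figure that may not apply to previously operated patients. Use abroad would carry the same gap.

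**Working it through.** **Inputs from 3.1.08.** Total operated on in the window, T = 70,000 to 100,000. Excluded for prior surgery, E = 25,000. Stated incident population, 45,000 to 75,000.

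**Assumed input.** RR is the risk of an adhesion-related readmission in excluded patients relative to retained patients, under the plan's own codes and over the same follow-up. The documents do not give it, so a range of 0.8 to 3 is shown.

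**Step 1: reproduce the plan's figure.** T − E: 70,000 − 25,000 = 45,000 and 100,000 − 25,000 = 75,000. Both match.

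**Step 2: excluded share.** f = E/T: 25,000/100,000 = 25.0% and 25,000/70,000 = 35.7%.

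**Step 3: count.** The share of all readmitted patients in the 2009–2011 surgical population that the cohort misses is f·RR / (1 − f + f·RR). For example, at RR = 1.5 and f = 0.25: 0.375 / (0.75 + 0.375) = 33.3%.

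**Step 4: per-patient rate.** The cohort rate divided by the rate in all surgical patients is 1 / (1 + f(RR − 1)). For example, at RR = 1.5 and f = 0.25: 1 / 1.125 = 0.889, or 11% too low.

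| Assumed RR | Readmitted patients missed, f = 25.0% to 35.7% | Cohort rate / all-patient rate, f = 25.0% to 35.7% |
|---|---|---|
| 0.8 | 21% to 31% | 1.05 to 1.08 (5–8% too high) |
| 1 | 25% to 36% | 1.00 (no bias) |
| 1.5 | 33% to 45% | 0.89 to 0.85 (11–15% too low) |
| 2 | 40% to 53% | 0.80 to 0.74 (20–26% too low) |
| 3 | 50% to 62.5% | 0.67 to 0.58 (33–42% too low) |

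The count is incomplete at every RR. The rate is too low only if RR exceeds 1.

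**Step 5: the two look-back rules.** Read literally, 3.1.08 and 4.3 select different patients. Someone operated on in early 2009 and again in 2010 is kept under 3.1.08 but excluded under 4.3. Someone operated on in 2004 and again in mid-2011 is excluded under 3.1.08 but kept under 4.3, because the gap is about seven years. The 25,000, and hence f, depends on which rule applies.

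**The case against.** The best defence is that 3.1.08 declares the incident restriction openly, while the burden sentence sits in a background section that asks for envisaged benefits. The onward uses are worded as possibilities, and no barrier or cost model is specified. The earlier Scottish result quoted in 3.1.07 is a per-patient proportion (34.6% over 10 years). If the update is reported the same way, the count shortfall does not arise and the bias is zero at RR = 1. This stands as to size, and it is why the rate column is shown. It does not remove the mismatch: a reader of 3.1.07 alone would take the estimate as covering all of Scotland's adhesion morbidity.

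A second defence is that repeat surgery is partly captured, because cohort members are followed through later operations and readmissions. That is true over time. But those events are already within the retained patients' risk and bring back none of the excluded 25,000.

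A third is that the broad group of possibly adhesion-related readmissions could push a burden figure upwards. That is a separate classification question and does not replace missing patients. It does mean that the net direction of error in a total burden figure is not settled.

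A reader might infer more than the documents support, in three ways:

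- **That everyone with earlier surgery is removed.** Only surgery within a five-year look-back excludes a patient; those with older operations stay in.
- **That the study is bound to understate the burden.** This is certain only for a count under the plan's codes. For a rate it needs RR above 1, which the reason for exclusion makes plausible but does not quantify.
- **That the true burden is about 1.3 to 2.1 times the study's figure.** That range is 1/(1 − missed share) for RR from 1 to 2. It rests on assumed ratios and on a raw count being reported as a national total, which the plan never says it will do.

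**Conclusion.** The mismatch is real: 3.1.07 claims an unrestricted national burden, and the cohort leaves out 25–36% of the surgical population for a reason tied to the outcome. Nothing in the supplied text adds these patients back, scales the estimate or limits the claim. The protocol sent for ethics approval, listed in Section 7, is not part of that text.

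As a count for the June 2009–June 2011 surgical population, the estimate misses 25–36% of readmitted patients at equal risk, and 33–45% or 40–53% at ratios of 1.5 or 2. As a rate, the error runs from none at a ratio of 1 to 20–26% too low at 2, with a 5–8% overstatement at 0.8. These figures rest on the plan's approximate 25,000 and 70,000–100,000 and on assumed ratios.

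The cohort is sound for the open versus laparoscopic comparison, and it can estimate readmissions after an initial operation. It would go too far to say that it can contribute nothing to a burden estimate. What it cannot do is supply the wider figure without scaling or a separate estimate for the excluded patients.

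**What to change.** 1. **Reconcile the look-back.** Sections 3.1.08 and 4.3 must give one rule, because the restated objective has to name it. This is a wording change, plus a check of which rule the extract used.

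2. **Restate the objective in 3.1.07.** Describe it as adhesion-related readmissions after an initial abdominal or pelvic operation, with none in the look-back period. State that this is not the total national burden, and that it must be scaled, with a sensitivity range for the rate ratio, before use in barrier or cost models or in other countries. The cost is wording only, and a narrower claim.

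3. **Where the extract can still be built or amended, also keep the previously operated patients as a flagged, separate descriptive stratum.** Leave them out of the open versus laparoscopic comparison and report burden with and without them. Processing must already identify these patients in order to exclude them, but the cost is not trivial: one derived flag that is not in the 4.3 variable list, about 25,000 more patients with their readmission records, and possibly an amended approval. Section 3.3.01 shows that access was by then being sought to answer journal editors' questions on presentation, so item 2 may be all that is practical. Even with this stratum, the result is the burden of the 2009–2011 surgical population. People operated on before June 2009 and not again in the window remain outside it, and the report should say so.

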### 4.3 Data Variables *Please read section 4.3 of the guidance*

Dataset/source Name	Variable	Time Period/Range	Processing only?
Anonymised ID			
Scottish Morbidity Record (SMR 01)	CHI	2004- Dec 2016	Yes
Scottish Morbidity Record (SMR 01)	Date of admission	2004- Dec 2016	No
Scottish Morbidity Record (SMR 01)	Sex	2009- Dec 2016	No
Scottish Morbidity Record (SMR 01)	Age (Date of admission- birth date)	2009- Dec 2016	No
Scottish Morbidity Record (SMR 01)	ICD-10 codes	2009- Dec 2016	No
Scottish Morbidity Record (SMR 01)	OPCS-4 codes	2009- Dec 2016	No
Scottish Morbidity Record (SMR 01)	Duration since index operation (date of admission from readmission - date of admission from index operation)	2009- Dec 2016	No
Scottish Morbidity Record (SMR 01)	Details of operation - laparoscopic/ open	2009- Dec 2016	No
Scottish Morbidity Record (SMR 01)	End of follow-up (month) (Date of end of follow-up, typically June 2016; however some patient might not complete follow-up because of mortality or migration)	2004- Dec 2016	No
Scottish Morbidity Record (SMR 01)	Continuous Inpatient Stay	2009- Dec 2016	No
CHI Database	Migration Month / year	2004- Dec 2016	No

NRS Deaths	Patient alive or death by end of follow-up	2004- Dec 2016 (measured in months, no date provided)	No
------------	--	---	----

Please justify your need for identifiable or potentially identifiable variables:

Identifiable data is only needed during the processing of data. Data will be collected during a range of 5 years from index surgery. Patients with a relevant OPCS-4 code as listed in the appendix are selected, if no prior such operation was found in the five years previous to the index operation. Identifiable information, NHS number and birth date are needed during processing to select reoperations that are definitely or potentially related to adhesion in patients following their index surgery. After processing these data can be removed. Age is potential risk factor for adhesions and will therefore be calculated.

4.4	NRS/NHSCR Data Sources Please read section 4.4 of the guidance	
Complete this section if access to NHSCR is required, or if there is any National Records of Scotland involvement		
4.4.01	Does the proposal require access to NHS Central Registry as a sampling frame for cohorts?	No
4.4.02	Does the proposal involve flagging of individuals on the NHSCR for long term follow up?	Choose an item.

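### Patients whose index admission already carries an adhesion code enter the incident cohort unflagged, so some later adhesion readmissions credited to the index operation may be existing disease.

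*Combined protocol and SAP*

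**What the plan says.** Section 3.1.08 defines entry by procedure: "Inclusion criteria are all patients undergoing initial abdominal or pelvic surgery between June 2009 and June 2011", and "Selection will be made by OPCS-4 codes related to the admission". It states one exclusion, "We will exclude patient who had had abdominal or pelvic operation in the 5 years before 2009", and gives the reason and closes the list in the same place: "as pre-existing adhesions from this prior surgery might influence results. There are no further exclusion criteria". Section 4.3 restates the rule with the look-back counted from the index operation, so that a patient qualifies "if no prior such operation was found in the five years previous to the index operation". That version also rests on surgery alone. The cohort is described as incident: "we expect an incident population of 45,000 to 75,000 to be included in the study".

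For a readmission to count as directly related, "an explicit adhesion reference was required in the operative OPCS-4 or diagnostic ICD-10 coding". No condition is placed on what was coded at the index admission. The index codes are available: "From the initial admission with abdominal or pelvic surgery we need ICD- 10 codes and OPCS- 4 codes describing the type of surgery performed". Their stated use is to describe the operation, and the only baseline characteristics requested are age and sex. Nothing in the text excludes, flags, stratifies or adjusts for an adhesion code at index.

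**The concern.** The plan accepts that adhesions present before the index operation can distort the results, but it screens for them only through recent surgery. Two kinds of patient pass that screen with adhesions already present: those operated on before the look-back began, and those whose adhesions have a non-surgical cause. If the index admission itself records adhesions, the code that defines the outcome is present at time zero. A later admission with the same code is then attributed to the index operation and to its route.

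Section 3.1.07 gives the study two main uses, and both are affected. One is an estimate of the current burden of adhesion morbidity, to be carried over to other countries and to models of adhesion barriers. The other is the comparison of open with laparoscopic surgery. The first can be inflated even if coded adhesions are balanced by route. The second is distorted if they are not. Dividing the cohort into three anatomical groups does not remove an imbalance within a group.

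**Working it through.** **The plan's own figure.** Section 3.1.08 expects 70,000 to 100,000 operated patients, of whom about 25,000 had prior surgery. 70,000 − 25,000 = 45,000 and 100,000 − 25,000 = 75,000, which reproduces the stated incident population. The subtraction removes prior-surgery patients only; nothing is taken off for adhesions coded at index.

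**Inputs that the documents do not give.** Let q be the share of the cohort with an adhesion code at index, and RR their risk of a directly related readmission relative to everyone else. Neither is stated. The only event rate, 34.6% over 10 years in the earlier study, pools direct and possible readmissions and is not split by index status, so it cannot supply RR. I assume q = 1%, 3% or 5% and RR = 2, 5 or 10.

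**Formulas.**
- Inflation of the crude risk, relative to patients without an index adhesion code: 1 + q(RR − 1)
- Share of all directly related events contributed by flagged patients: q·RR / [1 + q(RR − 1)]
- Apparent open/laparoscopic risk ratio with no true route effect: [1 + q_open(RR − 1)] / [1 + q_lap(RR − 1)]

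**Incidence.**

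| q | Patients flagged (of 45,000 / 75,000) | Cohort left | Inflation at RR 2 / 5 / 10 | Share of events at RR 2 / 5 / 10 |
|---|---|---|---|---|
| 1% | 450 / 750 | 44,550 / 74,250 | 1.01 / 1.04 / 1.09 | 2.0% / 4.8% / 9.2% |
| 3% | 1,350 / 2,250 | 43,650 / 72,750 | 1.03 / 1.12 / 1.27 | 5.8% / 13.4% / 23.6% |
| 5% | 2,250 / 3,750 | 42,750 / 71,250 | 1.05 / 1.20 / 1.45 | 9.5% / 20.8% / 34.5% |

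Example: q = 3% and RR = 5 give 1 + 0.03 × 4 = 1.12, and a share of 0.15 / 1.12 = 13.4%.

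**Route comparison, no true effect.**

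| q open / q laparoscopic | RR 2 | RR 5 | RR 10 |
|---|---|---|---|
| 3% / 3% | 1.00 | 1.00 | 1.00 |
| 3% / 1% | 1.02 | 1.08 | 1.17 |
| 5% / 1% | 1.04 | 1.15 | 1.33 |
| 1% / 3% | 0.98 | 0.93 | 0.86 |

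Example: 3% against 1% at RR = 5 gives 1.12 / 1.04 = 1.08. With the shares reversed it is 1.04 / 1.12 = 0.93. The sign therefore depends on which route carries more coded adhesions, and the documents do not say.

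**The case against.** The strongest points on the other side are these.

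*The text is an outline.* It is a data-access application. Section 7 lists the code appendix and the protocol sent for ethics approval as separate attachments, and neither is in the material available. Whether division of adhesions is itself an eligible index procedure cannot be checked. This stands as a limit. The point does not need it, because any listed operation combined with an adhesion diagnosis is enough for entry.

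*It is partly the look-back problem.* A patient operated on eight years earlier would be caught by a longer look-back. That is true, and the two issues overlap. But the data are requested only from 2004, and no look-back of any length catches adhesions with a non-surgical cause. The index codes can catch both, where adhesions are coded.

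*The later event may be new.* A reader might infer that every later adhesion readmission in these patients is recurrence wrongly counted. The documents do not support that: the index operation can itself create adhesions, and nothing requested separates old from new.

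*Burden is a legitimate target.* For a national burden figure these patients arguably belong in the count. This stands, and it argues against removing them from every result.

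*Exclusion has its own bias.* Section 3.1.08 concedes that adhesions are not always coded. If completeness of coding differs by route, dropping coded patients could itself select differentially, and an incidental operative finding would be treated like established disease. This also stands, and it favours reporting both ways.

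**Conclusion.** The gap is real and can be read directly from Sections 3.1.08 and 4.3: prior surgery is the only screen for existing adhesions, and the directly related outcome ignores what was coded at index. Applied as written, the plan counts patients already coded for adhesions as incident cases.

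The size is unknown. The 1% to 45% inflation spans the assumed grid and is not an estimate; the low corner is negligible and the high corner is not. A reader might also infer that the flaw would make laparoscopy look protective. That holds only if coded adhesions are more common in the open group. With equal shares and equal relative risk the ratio is undistorted, and with the opposite imbalance it moves the other way.

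The same mechanism could act in the possibly related class, where a symptom code such as abdominal pain may precede the operation. That class is deliberately broad, such a code at index need not mean adhesion disease, and no size has been worked out for it. It supports a secondary check only.

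**What to change.** Add to Section 3.1.08: *Index admissions carrying any code on the directly related adhesion list (ICD-10 or OPCS-4) will be flagged, and their number reported by route and anatomical group. The directly related incidence and the open/laparoscopic comparison will be reported both without them (incident population) and with them (all patients, for the burden estimate).*

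Optionally, report the possibly related class with and without readmissions whose only qualifying code was already on the index admission.

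The cost is one filter on codes already requested, one extra set of results, and an incident cohort smaller by an assumed 1% to 5%. No new variable is needed. The remedy is partial: adhesions left uncoded at index stay undetected, and because Section 4.3 requests ICD-10 codes only from 2009, adhesion diagnoses from earlier admissions would not be found either.
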